10. RISK AND RISK-BENEFIT RATIO

10.1 Risks from epicutaneous immunotherapy (EPIT).

In the previous pilot clinical study in cow’s milk-allergic children with a related drug product (patch test with the same technology as dialertest), there was no serious AEs reported during the trial and no child required interruption of treatment because of an AE. The expected Adverse reactions with Viaskin Milk during EPIT are described in the Viaskin Milk Investigator’s Brochure.

The potential risks observed in other Viaskin studies have been primarily localized dermatitis not considered serious in any subjects. There have been no reports of systemic reactions with Viaskin patch. But, if systemic reactions occurred in this study, the symptoms would be worsening EoE with abdominal pain and possible vomiting.

10.2 Risks from Upper Endoscopy and Biopsy.

The safety of multiple biopsies is supported by studies on adult patients with Barrett’s esophagus that have shown that multiple esophageal biopsies (as many as 35 to 120 esophageal biopsies in an individual patient) do not produce esophageal perforation or bleeding when performed by an experienced team of physicians, nurses, and technicians⁶⁸. In addition, a recent NIH study demonstrated that obtaining multiple mucosal biopsies for research purposes during elective endoscopy is well-tolerated and appears to have no more than minimal risk without appreciably increasing the risk of otherwise routine endoscopy⁶⁹. Importantly, there was no statistically

significant association between the number of biopsies, type of procedure, anatomic location of research biopsies, endoscopist, or the use of nonsteroidal anti-inflammatory drugs and the risk of complications.

The incidence of perforation associated with upper endoscopy was recently reviewed in an 11 year retrospective study at CHOP. A total of 21,345 esophagogastroduodenoscopy (EGD) were performed between February 1998 and November 2008 including patients with esophageal strictures or crepe-paper esophagus. Three perforations occurred with EGD (0.02%, 95% CI 0-0.04%), and 2 with colonoscopy (0.04%, 95% CI 0-0.11%). Two of the three EGD-related perforations occurred after therapeutic EGD (foreign body removal, and dilatation of a proximal esophageal stricture and esophageal web removal), for an incidence of 0.18% (95% CI 0-0.47%). **None of the EGD-related perforations was the result of esophageal mucosal biopsies.** The presence of crepe-paper esophagus or strictures does not increase the risk for EGD-related perforations based on this review, thus these patients were not excluded from our proposed cohort. Identified risk factors for perforation on diagnostic (non-therapeutic) endoscopy were Crohn's disease (2 colonoscopy perforations) and severe hemorrhagic gastritis (1 EGD perforation of the stomach). The incidence of perforation associated with pediatric gastrointestinal endoscopy performed by pediatric gastroenterologists in this case series from CHOP was low and less than that previously reported in adults. Based upon this retrospective study, the estimated incidence of perforation from EGD at CHOP is 1 in 7,115 EGD procedures.^{70,71}

There are standard risks from moderate intravenous sedation or general anesthesia for the one research biopsy. To minimize the risks, all anesthesia will be done by pediatric anesthesiologist. For the intravenous sedation, the risk of assisted ventilation is 0.1-0.2% and no patients have required intubation and no history of permanent injury based on current literature. For general anesthesia, the overall risk for a serious adverse event is 1/250,000. Total adverse events with nausea and vomiting being the most common are seen in 1/29 cases⁷²⁻⁷⁴.

Since the EGD procedure with biopsy is conducted under conscious sedation or anesthesia, this needs to be considered for the total risk assessment. The investigative team considers the overall risk of the single research EGD procedure with biopsy under conscious sedation or anesthesia to be at most a minor increase above minimal risk⁷⁵.

10.3 Risk-Benefit Ratio

While subjects in the active arm are in a study group that is exposed to greater than minimal risk, there is the prospect of direct benefit, in that these subjects may potentially be cured of milk-induced Eosinophilic Esophagitis or have reduced symptoms. Currently, the only therapy for this life-long disease is milk avoidance or off-label use of topical steroids. In addition, there will be additional knowledge gained about the disease and potential development of tolerance in Eosinophilic Esophagitis.

Both patients on the placebo arm and non-responders to therapy, we may have exacerbations of EoE symptoms including abdominal pain, and vomiting. To minimize this issue, we are using 3:1 randomization of active to placebo therapy. Also, we have incorporated a period of 1 week to 2 month to milk re-exposure to minimize symptoms of EoE.

The placebo arm will be at risk of the single research endoscopy with biopsy under sedation or anesthesia, which the investigative team believes is a minor increase above minimal risk. This arm will help inform the natural history of the disease and will serve as a meaningful control group. There is no treatment for the disease other than that outlined in section 6.2. Thus, avoidance of milk would be the continued recommendation for the placebo study arm. If the therapy is effective, the placebo subjects may benefit of the active treatment during the open-label treatment period.

In summary, the risks include application of Viaskin® Milk EPIT patches and the two research upper endoscopies and biopsies under conscious sedation or anesthesia. The main risk from the EPIT include rashes with local erythema or other local skin reactions, but serious adverse reactions cannot be excluded. Based on the experience at CHOP, the risk from upper endoscopy with biopsy under sedation or general anesthesia is a minor increase above minimal. Therefore, there is a prospect of direct benefit for the treatment arm with greater than minimal risk to these subjects, while there is no prospect of direct benefit for the placebo arm during the double-blind period, with minor increase above minimal risk.

11. METHODS OF ASSESSMENT

11.1 Medical History

Complete medical history will include history and duration of all allergies (including milk allergy) and current medical conditions, number of allergic reactions and treatments in the previous 12 months, past or present cardiovascular, respiratory, gastrointestinal, renal, hepatic, neurological, endocrine, lymphatic, hematologic, immunologic, dermatological, psychiatric, and genitourinary disorders, drug and surgical history and any other diseases or disorders.

11.2 Pregnancy Test

Pregnancy will be determined by evaluation of urine pregnancy tests. Subjects who are pregnant at screening are excluded from the study. Subjects who become pregnant during treatment must be discontinued from the study.

The Principal Investigator will collect information on any female subject who becomes pregnant while participating in this study. The subject will also be followed to determine the outcome of the pregnancy.

11.3 Physical Examination

Physical examinations will be performed by a physician or nurse practitioner and will include examination of the following: general appearance, head, ears, eyes, nose and throat, neck, complete skin examination, cardiovascular system, respiratory system, abdominal system and nervous system. For each body system an assessment of normal or abnormal will be recorded in the eCRF at screening and the abnormality will be documented. During the study, any clinically relevant changes observed during physical examinations will be reported as AEs.

Physical examinations must be performed before the upper endoscopy/biopsy.

11.4 Vital Signs and Weight

Vital signs will include sitting systolic and diastolic blood pressure, heart rate, respiratory rate and temperature. Systolic blood pressure and diastolic blood pressure will be measured on the same arm after the subject has been in a sitting position for 5 minutes. Heart rate will be recorded simultaneously with blood pressure measurements, followed by respiratory rate and body temperature.

Body weight (kg) will be measured without shoes or jacket. Height (cm) will be determined at screening.

During the study, the measurement of vital signs may be repeated at the discretion of the Investigator for safety reasons. Clinically relevant abnormal findings will be reported as AEs.

Vital signs must be performed before the upper endoscopy/biopsy.

11.5 Eosinophilic Esophagitis Quality of Life

Quality of life is a measurement of a subject's overall well-being. QOL will be measured by the validated age specific Eosinophilic Esophagitis tool for 5-7 years of age, 8-12 years of age, and 13-18 years of age (Appendix 2) developed by Franciosi and colleagues, based on the age of the subject at Visit 2. The subjects will complete the same questionnaire throughout the study.

11.6 Clinical Laboratory Testing

Venous blood samples will be taken for hematology and biochemistry testing. The following parameters will be determined:

Hematology: hemoglobin, hematocrit, platelets, red blood cells, white blood cells.

Biochemistry: aspartate aminotransferase, alanine aminotransferase, total bilirubin, total protein, blood urea nitrogen, creatinine.

Analysis of blood samples will be conducted by CHOP laboratory. Fresh blood will be collected from the above described patients per above protocol. Blood (max lesser of 50 ml or 3 ml/kg in a 6-8 week period) will be obtained by venipuncture during outpatient visit or obtained by IV during endoscopy procedure. Blood will be collected only after informed consent/assent is given. Participants will be given an opportunity and the time of consent to opt in or opt out of future use in subsequent research. The estimated volume of blood collected from each subject during the entire (22 month) study will be approximately 215mL. Additional and repeat laboratory safety testing may be performed at the discretion of the Investigator.

11.7 Research Laboratory Testing

Research labs include TSLP, Epigenetics, and T cell studies. They will be processed and stored at the [name] Research Laboratory at the Children's Hospital of Philadelphia.

11.8 Upper Endoscopy with Biopsy

All subjects will undergo a minimum of four upper endoscopies with biopsies during their participation in the study (two each of proximal and distal, plus any inflamed areas) as per standard clinical practice: at least two at Screening as Standard of Care (Visit 2 and Visit 3) and two at the end of each treatment period as Research (Visit 10 and Visit 16). The results of additional SOC endoscopies will be allowed to assess eligibility, if the endoscopies are required for clinical care purposes. The samples will be processed by the Department of Pathology at The Children's Hospital of Philadelphia and the number of eosinophils will be counted using hematoxylin and eosin stain. The handling of samples will be done following ASGE Standard on Endoscopic Mucosal Tissue Sampling.⁶⁷

Upper endoscopy will be scored using a validated standardized measure.⁵⁷ The measure examines four major esophageal features (rings, furrows, exudates and edema) and the presence of minor features of narrow caliber esophagus, feline esophagus, stricture and crepe paper esophagus. The features are graded:

- Rings (0-none, 1-mild, 2-moderate, 3-severe)
- Exudates (0-none, 1-mild, 2-severe)
- Furrows- (0-mild, 1-present)
- Edema- (0-mild, 1-present)
- Stricture (0-mild, 1-present)
- Crepe paper esophagus (0-mild, 1-present)

11.9 Histological Evaluation

Prior to randomization, esophageal biopsy samples will be evaluated to confirm eligibility. Biopsy samples will be stained with hematoxylin and eosin stain. Intraepithelial eosinophils will be counted in all HPFs using 400X light microscopy. A HPF will be counted only if at least half of the field is occupied by tissue. The maximum eosinophil count per HPF will be reported for each esophageal biopsy site (at each of 2 levels). In addition to the evaluation for eosinophilia, all biopsy samples will be assessed for other histologic changes including epithelial hyperplasia, intercellular edema, and fibrosis. Histologic evaluation to be completed by a blinded Pathologist at CHOP.

At the end of each treatment period (Visit 10 and Visit 16), the esophageal biopsy specimens from all subjects will be evaluated in a blinded fashion by an independent pathologist. Specimens will be examined with respect to the maximum eosinophil counts and other histologic changes. Together with the EoE Clinical Symptom Score, the maximum eosinophil count per HPF for each specimen (from the total of all specimens) will be used to determine response to treatment.

The maximum eosinophil count will be defined as the highest number of eosinophils observed in any single HPF from an esophageal specimen. All specimens from all esophageal sites will be considered in determining the resolution of eosinophilia. A maximum eosinophil count will be recorded for the esophagus. The highest peak counts at a given timepoint (screening or end of each treatment visit) will be referred to as the maximum eosinophil count for that timepoint. The

mean Esophageal Eosinophil count will be the mean score of each of the high power fields from the all biopsy specimens.

As a confirmatory marker of EoE disease activity, we will use paraffin-embedded esophageal biopsies already obtained for routine clinical care to identify innate immune cell populations as well as chemokine expression through immunohistochemistry staining.

11.10 Diet Diary

Subjects will indicate the duration and amount of milk and milk products taken on a daily basis during the screening period and once milk is re-introduced into the subject's diet during the treatment period (Milk reintroduction at Visit 9 and Visit 15).

The milk introduction period and amount of milk and milk products taken should be the same, as much as possible, at both timeframes.

11.11 Subject Diary

Diary cards will be provided to each subject. Subjects will be asked to record on a daily basis in their diary cards for the first 3 months the time of application and removal of each Viaskin®, along with reason(s) for early removal (should that occur) and any observed AE(s) to the Viaskin® (local and/or systemic) or any other AEs. After 3 months, the subjects are instructed to report only the day/period when the patch was not applied as per protocol. Subjects will also be instructed to record any concomitant medication or treatment taken for any type of AEs.

The diaries may also be used to record the dietary information during the milk reintroduction periods at screening and at the end of treatment. In addition, the diary cards will also be used for the subjects to report any accidental consumption of milk that could have occurred in the study, during the milk-diet required period.

Subjects must bring their diary back to the Investigator at each visit, and the Investigator must check the diary for completeness and accuracy. It is the Investigators' responsibility to instruct the subject about the use of the diary, and to ensure that the subject completes the diary accurately. Any problems with completing the diary will be addressed with the subject. Completed pages of the diary cards will be collected and kept by the investigator at each visit. The remaining blank pages of the diary cards will be given back to the subject at each visit before discharge. All diary cards must be returned at completion of the study, or if the subject discontinues.

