The time of application and removal of each Viaskin® will be noted on the subject diary cards (see Section 10.10), along with any observed AE(s) (local and/or distant). Application of the Viaskin® at a similar time for each application (am or pm) is recommended.

After Visit 10, all subjects will continue treatment with open-label Viaskin® Milk 500 µg for up to 11 additional months. It is permitted at the discretion of the Investigator, to postpone the application of the first patch up to a maximum of 7 days after V10.

To increase the safety of subjects at the beginning of the open-label treatment period, in particular for subjects crossing over from placebo to the active Viaskin Milk treatment, the daily duration of application will again be adapted from Visit 10 for the first weeks of treatment: 6 hours/day during the first week, 12 hours/day during the second week, and for an entire 24 hours daily from the third week onwards. During the period of 24 hours of daily application, flexibility of 24 hours ± 4 hours of daily application is permitted.

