9.7 Visit 9: Treatment Period; Month 9 (\pm 14 days)

The following assessments/procedures will be performed:

- Physical examination (including a complete skin examination).
- Vital signs (including heart rate, blood pressure, respiratory rate, and temperature).
- Eosinophilic Esophagitis Symptom Score (see Section 11.12)
- **Milk reintroduction (similar amount and duration as done during the screening period)** while the subject is on a proton pump inhibitor.
- Dietary History.
- Record all AEs (volunteered or in response to an open question).
- Record all concomitant medication(s).
- Dispense diary cards (re-instruct subject on use if necessary).
- Review 'diary' and ensure that the diary has been completed accurately and that the subject is comfortable with using the diary.
- Check unused medication and assess medication compliance.
- Dispense the new treatment box to subject. Apply one Viaskin® patch to subject.
- Check skin under the Viaskin® and grade any local skin reaction (see Section 11.13).
- Take a photograph of site(s) of application of Viaskin® and keep in the subject's medical records or source documents.

9.8 Visit 10: Treatment period; (1 week to 2 months after Visit 9, 3rd endoscopy)

Subjects will have an upper endoscopy and biopsy performed at this visit. They will have an upper endoscopy from 1 week to 2 months after reintroduction of a minimum of 30 ml of milk

daily into their diet, and while on proton pump inhibitor, as done during the screening period. When the subjects are symptomatic, they will have an endoscopy 1-2 weeks after symptoms occur.

The milk consumption should be equivalent to what the subjects were taking at the beginning of the study.

Visit 10 corresponds to the last day of double-blind treatment and the start of open-label treatment period. Standard Operating Procedures will be followed for endoscopy procedure⁶⁷. Patients will need to be healthy for this procedure. Any subject who has had a viral upper respiratory infection or gastroenteritis within 7 days will need to be rescheduled.

The following assessments/procedures will be performed:

- Physical examination (including a complete skin examination).
- Vital signs (including heart rate, blood pressure, respiratory rate, and temperature).
- Eosinophilic Esophagitis (Age-specific) Quality of Life Measure (Appendix 2)
- Eosinophilic Esophagitis Symptom Score (see Section 11.12)
- Blood collection for laboratory tests (hematology, biochemistry)

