13.6.6.1 Adverse Events

All AEs will be coded by system organ class and preferred term using MedDRA. Treatment-emergent AEs (TEAEs) will be defined as any AEs, regardless of relationship to study drug, which occur during AE collection period of study drug or any event already present that worsens in either intensity or relationship to study drug following exposure to the Viaskin®. If relationship information is missing, the TEAE will be considered drug-related.

An overall summary of TEAEs will be provided showing the number and percentage of subjects in each treatment group with any TEAE, any potentially drug-related TEAE, any severe TEAE, any serious TEAE, any TEAE leading to discontinuation, and any TEAE leading to death. The number of events will also be presented.

The number of AEs as well as the number and percentage of subjects who experienced at least one AE will be summarized by system organ class, preferred term and treatment group. The incidence of the following events will be summarized:

- Local skin tolerance: incidence, severity and duration of local TEAE at site of Viaskin® application as reported by subjects in the diary card
- TEAEs: incidence, severity and duration.
- Potentially drug-related TEAEs
- Discontinuations due to TEAEs
- Laboratory data, physical examinations, and vital signs Systemic allergic symptoms in the active and placebo groups
- Potentially drug-related systemic allergic symptoms
- SAEs
- Potentially drug-related SAEs

In addition, TEAEs will be summarized by relationship to study drug and by severity. If a subject has more than one occurrence of the same TEAE with different severities or relationship to study drug, then the TEAE will be assigned to the highest severity category and/or most related relationship category. If the intensity or relationship is missing, then the 'worst case' will be assumed (i.e., severe for intensity and drug-related for relationship).

The proportion of subjects that experience systemic allergic symptoms will be summarized by treatment. All TEAEs will be listed.

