#### **2.2.6 Safety endpoints**

The safety endpoints are:

- a. Local skin tolerance: incidence, severity and duration of local Treatment-Emergent Adverse Event (TEAE) at site of Viaskin® application as reported by subjects in the diary card.

- b.** Potentially drug-related TEAEs.
- c.** Discontinuation due to TEAEs.
- d.** Laboratory data, physical examinations, and vital signs.
- e.** Systemic allergic symptoms and relatedness to Viaskin®.
- f.** Potentially drug-related systemic allergic symptoms.
- g.** SAEs.

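### Daily diary entries stop at month 3 and are not restarted at Visit 10, so the diary-based local-tolerance endpoint has no daily record of first active exposure in placebo subjects who cross over

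*Protocol*

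**What the plan says.** **Diary content.** Protocol 11.11 tells subjects to "record on a daily basis in their diary cards for the first 3 months" the application and removal times of each patch, reasons for early removal, and any adverse events. It continues: "After 3 months, the subjects are instructed to report only the day/period when the patch was not applied as per protocol". The sentence after that, which has no time limit, also has them record medication or treatment taken for adverse events.

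**Endpoint.** Protocol 13.6.6.1 lists "Local skin tolerance: incidence, severity and duration of local TEAE at site of Viaskin® application as reported by subjects in the diary card". SAP 2.2.6(a) uses the same definition, "at site of Viaskin® application as reported by subjects in the diary card". Protocol 8.6.2 adds that the duration of local events is the subject's own assessment.

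**Crossover.** Section 9.8 states: "Visit 10 corresponds to the last day of double-blind treatment and the start of open-label treatment period". Section 8.5.1 repeats the stepwise increase in wear time from Visit 10, "in particular for subjects crossing over from placebo to the active Viaskin Milk treatment". The procedure lists for Visits 10 to 16 dispense and review diary cards and allow re-instruction if it is needed. None says that daily entry resumes.

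**Texts with no time limit.** Section 8.5.1 has patch times and observed adverse events noted on the diary cards, and points to a Section 10.10 that the protocol does not contain (the diary is Section 11.11). The synopsis and SAP 2.1 say that safety data are reported on diary cards between visits.

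**The concern.** A diary-based endpoint can be no better than the diary. For the 16 planned active subjects, the first three months on milk protein are the months of daily recording. For placebo subjects those same daily entries describe an inert patch. Their first contact with milk protein comes at Visit 10, when 11.11 asks only for departures from patch application and for treatments taken. First exposure is thus recorded differently by original arm, at a moment that the protocol itself treats as a new start.

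Section 10.3 names local skin reactions as the main risk of the patch, and Section 12.11 makes Grade 4 reactions events of special interest. What is at stake is how completely a descriptive safety endpoint is measured, above all the onset and duration of reactions that begin and end between visits.

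**Working it through.** The plan states no figure on this point, so there is none to reproduce. The check is a timeline and a comparison of data sources.

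**Timeline** (1 month = 365.25/12 = 30.44 days)
- Daily entry lapses at 3 × 30.44 ≈ day 91 (11.11).
- Visit 9 is at Month 9 ± 14 days, and Visit 10 is 1 week to 2 months after Visit 9 (9.7, 9.8).
- Earliest Visit 10: 273.9 − 14 + 7 ≈ day 267, which is 176 days or 5.8 months after the lapse.
- Nominal Visit 10 (Month 11): ≈ day 335, which is 244 days or 8.0 months after.
- Latest Visit 10: 273.9 + 14 + 60.9 ≈ day 349, which is 258 days or 8.5 months after.
- The extra 21 days that Section 9.13 allows are not used; adding them at the late end would widen the gap.

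No placebo subject on schedule can receive a first active patch while daily entry is required.

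**Coverage of treatment time on the 11.11 wording**
- Double-blind: 3 of 11 months. Open-label: 0 of 11 months. Overall: 3/22 = 14%.
- With a three-month restart: 6 of 22 months = 27%.
- The lapse also covers double-blind months 3 to 11 in both arms.

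**Subjects affected.** At most 6 of 22 planned = 27%. This is a different ratio from the month count above. It is a ceiling, because a placebo subject who leaves before Visit 10 never receives an active patch, and the plan expects 18 completers.

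**Sources of local-reaction data at first active exposure**

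| Source | Active arm, from Day 1 | Crossovers, from Visit 10 |
|---|---|---|
| Daily diary entry of adverse events | First 3 months (11.11) | Not stated |
| Diary entry of treatment for adverse events | Yes (11.11) | Yes (11.11) |
| Clinic skin grading | Day 1, Day 8, Months 1, 3, 6, 9 | Day 8, Months 1, 3, 6, 9 after Visit 10 |
| Photographs | Day 1, Day 8, Months 1, 3, 6, 9 | Visits 11 and 15; none listed for Visits 12 to 14 (9.10, Table 3B) |
| Calls | Monthly from Visit 5 | Monthly to Visit 16; Table 3B marks adverse events |

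**How well Visit 11 covers the first days.** Visit 11 is 8 ± 3 days after Visit 10, so day 5 to day 11. The first open-label patch may be postponed by up to 7 days (8.5.1, 9.8). With full postponement Visit 11 falls between 5 − 7 = −2 and 11 − 7 = +4 days from first active exposure. The next graded visit is Month 1 ± 7 days. In that case much of the early wear-time increase passes without a clinic skin check.

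**The case against.** The strongest reply is that the crossover is well watched. Visits at Day 8 and Months 1, 3, 6 and 9 are repeated after Visit 10, with skin grading and adverse-event questions at each. Table 3B marks adverse-event collection at the monthly calls as well as at the visits. Treated reactions still leave a diary entry. Cards are dispensed again at Visit 10, and three other texts can be read as open-ended diary reporting. All of this stands, and it rules out several stronger readings that a reader might infer:

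- *That durations can be reconstructed only at clinic visits, with two to three months of recall.* The monthly calls bring the planned open-label recall gap to about one month.
- *That the protocol takes no extra care over recording at crossover.* Visit 11 falls early in open-label treatment and includes grading, a photograph, adverse-event recording and diary review.
- *That open-label tolerance would look better than double-blind tolerance.* No such comparison is planned. Safety has no formal analysis (Protocol 13.6.6, SAP 4.5), and SAP Tables 17 to 20 are not split by period. On the 11.11 wording, daily entry also lapses for most of the double-blind period.

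What the reply does not supply is a daily record. Grading is a snapshot and calls rely on recall; neither fixes when a reaction between visits began or ended. The open-ended sentences in 8.5.1, the synopsis and SAP 2.1 conflict with the word *only* in 11.11. The one in 8.5.1 refers the reader to a diary section, and none provides a restart.

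**Conclusion.** The point holds in a limited form. On the text of Section 11.11, the diary-based local-tolerance endpoint has a daily record of first active exposure for the active arm and none for the crossovers: at most 6 of 22 planned subjects, with Visit 10 falling 5.8 to 8.5 months after daily entry ends. Capture in that group is reduced, not absent. The weakness lies in onset and duration between visits.

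This rests on two assumptions: that 11.11 governs over the general sentences elsewhere, and that *first 3 months* means the first three months of treatment and not of each period. If sites have read either differently, the conflict in wording remains but the data loss may be smaller. The documents give no rate of brief or untreated local reactions, so the amount of under-recording cannot be calculated. Primary efficacy, sample size and power are unaffected. This is an inexpensive improvement, not a threat to the trial's main result.

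**What to change.** - **Protocol 11.11:** restart daily entry of patch times and adverse events for 3 months from the first open-label patch. Count from that patch and not from Visit 10, because it may be postponed. Apply the restart to all subjects; limiting it to former placebo subjects would reveal the original allocation. State in the Visit 10 list that daily entry resumes.
- **Consistency:** align the synopsis, Protocol 8.5.1 and 11.11, and SAP 2.1 on what the diary collects and for how long, and correct the cross-reference in 8.5.1.
- **SAP:** summarise local treatment-emergent events by time since first active patch (Day 1 for the active arm, first open-label patch for the placebo arm). State that double-blind months 3 to 11 have no daily adverse-event entries.

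The cost is protocol and SAP wording, plus three more months of daily entries for families. Cards are already dispensed at these visits, so no visit or procedure is added. Daily records cannot be recovered for subjects who crossed over before the change; the report should say so.
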